Detailed Care Group Focus Group Sampling: At the beginning of a Care Group Meeting, the RA will explain that she will be conducting a short focus group. The RA will read the FOCUS GROUP RECRUITMENT SCRIPT and ask for interest to participate. The RA will invite all present members of the Care Group who express interest to participate in a focus group. The RA will read the INFORMED CONSENT and SHORT FORM to each of the chosen participants separately. The RA will obtain participant written consent with the SHORT FORM, separately and privately, and will invite them into the private focus group area and introduce them to the observers.

Aim 3: Evaluate the impact of the intervention on initial screening uptake and re-screening rates. (See Table 4)

TABLE 4: Aim 3 - Initial & Sustained Change Data Collection

Methodology			Measures	Variables
Quantitative	g Document Review DCI: 1612	No human participants. Review of aggregated health service records.	Initial Uptake/ Sustained utilization	
A. Number/% of women screened for the first time, age stratified 1
 
B. Number/% of women being re-screened, age stratified
 
C. Number/% of positive screened women referred/treated (aggregated data only)

	a Individual Interval Interview DCI: 1603, 1604	Systematic sampled individuals followed over time. Sample size: n = 0 new of sample a		

To achieve aim 3, we will follow cluster-wide trends through aggregated health service data⁶⁹ and participant-level impact through individual interviews. **Health service data** (# of initial and re-screenings stratified by age and number of referred women who completed treatment) will be reported by each cluster to the district center through the standard reporting structure. These de-identified data are reported to the regional level where they will be collected. Through the individual interviews described in aim 1 above (Table 2), we will collect impact data within our participant population in the form of first-time and re-screenings.

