6.0 Data Analysis and Statistical Considerations

Quantitative Analysis: All survey and interview data will be presented using basic descriptive statistics such as the frequency, % and mean (SD). To compare the intervention effect (screening rate, awareness, etc) within same participants before and after the intervention, Mixed-effects logistic regression model will be utilized. The mixed-effect model will also account for multilevel clusters such as households and districts. The between-subject effects to compare the impact of different regions with and without intervention implemented treating them as intervention and control group will be tested using Chi-squared test for single level samples and mixed-effects logistic for multilevel data. Outcome related factors such as demographic information and other barriers will be measured using descriptive statistics and to test the intervention effect by using multiple regression models.

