
Mixed methods Analysis and Writing. Mixed methods involves integrating the multiple types of data using well-accepted designs including: triangulation, explanation, transformation, and exploration.⁷⁵ We will use both SAS and Atlas/ti to further analyze data that will have already been collected, coded, and analyzed. Key to this integrated analysis is looking for intersections across levels that may explain: **1)** Which access facilitators best address barriers to seeking cervical cancer screening services among women who are most at risk? **2)** What benefits do interventions at each level of intervention (individual, household, or community) provide? **3)** What role does gender or age play in affecting barriers to accessing screening? **4)** What are the most influential sources that change motivation of screening eligible women change over time? **5)** What will most likely predict

that screening eligible women recommend screening to their peers? The analyzed data will be used to generate mixed methods publications responding to these key themes and will add to the body of knowledge for improving initial uptake and sustained utilization of cervical cancer screening services.

Power calculations

Clusters and Population: There will be three clusters comprising separate districts (Kedougou, Salemata, and Saraya) in Kedougou. Using two independent proportion method of cluster randomization power analysis (PASS13), to obtain the power 80% under significance level 0.05, the 10% difference of the screening rate with assumed ICC 0.01 requires n=15 per each of 3 clusters. Tables 2, 3, and 4 outline the data collection methodology for each aim. These data will be collected within each cluster at baseline and every six months - coinciding with a crossover of a new (random) cluster. Our selected sites are comprised of zones representative of region including rural, district center, semi-urban, and urban. Contamination is unlikely given distance (the distance between sites ranges from 32 kilometers / 45 minutes by car to 3 ½ hours by car).

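### Section 6.0 allows a chi-squared test for single-level samples when comparing areas with and without the intervention, but no sample in this three-district design is single level, so the test understates uncertainty

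*Protocol*

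**What the plan says.** The quantitative analysis paragraph of protocol section 6.0 describes two comparisons. For change within the same participants it plans a mixed-effects logistic model, and adds: "The mixed-effect model will also account for multilevel clusters such as households and districts". For the between-subject contrast, the aim is to "compare the impact of different regions with and without intervention implemented treating them as intervention and control group", tested by a "Chi-squared test for single level samples and mixed-effects logistic for multilevel data". The paragraph does not say which data count as single level.

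The power paragraph in the same section states "There will be three clusters comprising separate districts (Kedougou, Salemata, and Saraya) in Kedougou" and assumes an ICC of 0.01 ("the 10% difference of the screening rate with assumed ICC 0.01 requires n=15 per each of 3 clusters"). The significance level is 0.05.

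Section 3.0 describes the data. Each cluster has three sites. Interviewees are drawn from households or Care Groups within sites and are interviewed six times. For Aim 3, screening counts come as aggregated health service records reported by cluster: "These de-identified data are reported to the regional level where they will be collected".

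**The concern.** The intervention is switched on for whole districts. Every woman interviewed and every facility count belongs to a district, so a contrast of areas with and without the intervention is always a contrast of districts. A chi-squared test on individuals treats each woman as if she had been allocated independently, which sets the between-district variance to zero. An ordinary difference in screening between one district and the other two can then appear as an intervention effect.

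Aim 3 is the impact aim of the study, and the protocol hopes its findings will inform national policy. Section 6.0 offers a clustered and an unclustered test of the same contrast without saying when the second applies, and the unclustered one overstates significance.

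**Working it through.** **The plan's own figures.** The protocol gives no error rate for the chi-squared test beyond the nominal 0.05. Its only related calculation is the sample size of 15 in each of 3 clusters. That figure could not be reproduced: even 0% versus 10%, one-sided and without clustering, needs 58 per arm. It is a separate matter and is not used below, except that its ICC of 0.01 is taken as given.

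**Is any sample single level?**
- Baseline survey and interval interviews: person within household or Care Group, within site, within district, with repeated rounds.
- Facility records: women within facility, within district, reported as counts.
- Allocation: three districts.

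None qualifies.

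**Formula.** Take m women in each of three equal districts, one district against two (or two against one), no true effect and a two-sided 5% test (sidedness is not stated; two-sided assumed). The true variance of the difference in proportions is the naive variance multiplied by the design effect DE = 1 + (m − 1) × ICC. The actual type I error of the unadjusted test is then 2 × [1 − Φ(1.96 / √DE)].

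**Inputs for m.**
- 45 and 75 women per cluster: Table 2 (interval interview and baseline survey).
- 240-300: 80-100 households per Care Group (section 3.0, household recruitment) × 3 sites, assuming one eligible woman per household.
- 3,393: 509 women screened in 2014, roughly 5% of those targeted (section 1.0), gives 509 / 0.05 = 10,180; divided by 3, equal districts assumed.
- 6,102: 18,305 women with access region-wide (section 1.0, preliminary work) divided by 3, equal districts assumed.

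**Results.**

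| m per district | DE, ICC 0.01 | Error, ICC 0.01 | Error, ICC 0.001 |
|---|---|---|---|
| 45 | 1.44 | 10.2% | 5.5% |
| 75 | 1.74 | 13.7% | 5.9% |
| 240 | 3.39 | 28.7% | 7.8% |
| 300 | 3.99 | 32.6% | 8.5% |
| 3,393 | 34.92 | 74.0% | 35.0% |
| 6,102 | 62.01 | 80.3% | 46.2% |

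Example: m = 75 and ICC 0.01 give DE = 1 + 74 × 0.01 = 1.74, √1.74 = 1.319, 1.96 / 1.319 = 1.486, and a two-sided tail of 13.7%.

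**Simulation check.** Beta-binomial draws for three districts agree with the formula to within about 1 percentage point at ICC 0.01 and m of 240 or more. In small samples with a 5% screening rate, sparse counts make the chi-squared test somewhat conservative. At ICC 0.01 the simulated error is then 7.6-7.8% at m = 45 and about 12% at m = 75, which gives the lower ends of the 8-10% and 12-14% ranges. At ICC 0.001 and a 5% rate, the simulated error is 4.2% at m = 45 and 5.3% at m = 75, so there is essentially no inflation on the interview sample.

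**Where the error reaches one half.** This needs 1.96 / √DE = 0.674, so DE is about 8.45. At ICC 0.01 that is about 746 women per district; at ICC 0.001 it is about 7,445.

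Repeated interviews of the same women would add further correlation if rounds were pooled. The table does not include this.

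**The case against.** The strongest reply is that the sentence contains its own safeguard. It sends multilevel data to a mixed-effects logistic model, and the paragraph names households and districts as levels. If nothing here is single level, the rule routes everything to the mixed model and the chi-squared test is never run. That stands to this extent: the text is a conditional rule with an empty branch, so the ICC of 0.01 in the power paragraph is not flatly contradicted, and harm arises only if someone classes clustered data as single level. It does not save the branch. The plan writes it in for this very contrast and does not say what falls under it.

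A reader might infer that the single-level data are the Aim 3 facility counts, and hence that the test would declare false effects about half the time or more. The documents do not support this. Section 6.0 never assigns the chi-squared test to facility counts; its paragraph opens with survey and interview data and speaks of between-subject effects. The protocol gives no catchment size for the nine study sites, and the region-wide figures are not theirs. Even on facility counts, an error of one half needs roughly 750 women per district at ICC 0.01, and it is not reached at ICC 0.001 with the largest denominator the protocol offers.

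It is also fair to say that deleting the test does not cure having only three clusters.

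**Conclusion.** The concern holds in a limited form. The chi-squared branch is wrong as written for any comparison of districts with and without the intervention. At the protocol's own ICC, type I error on the interview sample is about 8-10% with 45 women per district and 12-14% with 75, roughly two to three times nominal.

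Larger figures are conditional on the test being applied to facility counts, which is an inference: about 29-33% with Care Group coverage as denominator, and 74-80% with region-wide figures split equally. At ICC 0.001 these fall to about 8-9% and 35-46%. All figures assume equal district sizes and a one-versus-two contrast. The structural conclusion needs none of these numbers; only its size depends on them.

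**What to change.** In section 6.0, delete the chi-squared test for any comparison of districts with and without the intervention. State that this contrast will be analysed only by a method that accounts for district, and also for site and period.

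For facility counts, model first-screen rates by site and period, with site and period effects, where an eligible-women denominator is available. Where only a one-versus-two-district contrast is shown, report the district rates and their difference without a p-value computed from individual women.

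The edit is one or two sentences. Two costs should be stated openly:
- The protocol gives no eligible-women denominators by site, so these may have to be obtained.
- Inference from between-district variation is very limited with three districts. A single-period contrast of three district summaries has 3 − 2 = 1 degree of freedom, and a permutation test over the 3! = 6 crossover orders cannot give a p-value below 1/6, or about 0.17. The between-district result may therefore be mainly descriptive, and the protocol should say so in advance.

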Overview of Study Data Collection: To achieve all aims, we will conduct a cluster-randomized stepped wedge study across three representative clusters (each containing a district center and two rural sites) in the Kedougou region. For each aim we will collect data at baseline and at 6-month intervals in each cluster (data collection intervals coincide with the initiation of the intervention in a new cluster). In aim 1, we will develop (through a participatory approach), pilot, and conduct surveys and interviews of eligible clients as well as focus groups (FG) (women ages 30-44 and 45-59) and interviews of men (ages 30-59). For aim 2, we will describe the development, piloting, implementation, and adaptation of an aim 1-informed context-specific multi-level peer education curriculum across clusters through the stepped wedge approach^{59,60} in the Kedougou region. We will collect quantitative program reach data and qualitative process evaluation data at each time period. These data will be used to adapt the intervention over time. To achieve aim 3, we will collect aggregated health service level utilization data and individual surveys.

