TABLE 2: Aim 1 - Demand-Side Access Data Collection

		Methodology	Measures	Variables
Quant	a	Individual Baseline Survey BL / End DCI: 1601, 1602	Systematic sampled individuals (Women: 75 / cluster) (Men: 30 / cluster) Sample size: n = 315	Demographics: # of people / roles in household, genders, # of eligible women, # of women seeking screening, health seeking decision making process / power, cost concern, facility proximity, health practices and opinions, knowledge and opinions of partners of eligible clients.
	b	Individual Interval Interview DCI: 1603, 1604	Systematic sampled individuals (Women: 45 / cluster) (Men: 30 / cluster of sample a)	Socio-demographics: Age, gender, marital type/status, education level Behavioral risk factors: Sexual debut, lifetime sexual partners, gravity, parity, age at first birth, number of children, smoking status, diet Clinical risk factors: History of STI, weight, long-term oral contraceptive use Health literacy / seeking: Cervical cancer screening history & knowledge, preventative care opinions, health service utilization
Qual	C	Women's Focus Groups DCI: 1605	Purposive-sampled groups (women, 30-44 or 45-59) of sample a	Demand-side access ref Instruments ⁴² Ability to perceive: Health literacy, Health beliefs, Trust and expectations Ability to seek: Personal and social values, culture, gender, autonomy Ability to reach: Living environments, Transport, Mobility, Social support Ability to pay: Income, Assets, Social capital, Health insurance Ability to engage: Empowerment, Information, Adherence, Caregiver support

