To achieve Aim 1, we will orient 3 CGs in each cluster. Through a participatory process involving CG leaders, health service leaders, midwives, and community members (women and men) we will develop, field test, and refine quantitative individual-level surveys that gather access barriers data corresponding to the variables listed in Table 2. We will conduct quantitative **a) Individual Baseline Surveys** with the same enrolled women (up to 25) and the same 10 men in each site per cluster. These data will be collected at baseline and at the end of the study period (after 3 years). We will also conduct **b) Individual Interval Interviews** with the same women (up to 25) and the same 10 men in each site per cluster. These data will be collected at baseline and every six months through the end of the study period (after 3 years). Therefore, these data will be collected six (6) times. These pre-tested, approved standard individual-level questionnaires (close ended) will be administered (face-to-face) by an RA of the same gender as the participant in the participants' preferred language (Malinke, Pulaar, or French). We will also conduct **c) Women's Focus Groups**. Through these FGs we will collect qualitative data, from women stratified by age, describing demand-side access barriers and facilitators (Table 2). The Research Assistant will moderate the 45 minute FGs in the preferred language (Malinke, Pulaar, or French) and two PCVs will observe and record written observations in real time. We will audio record the sessions (to be transcribed into both French and English). The Research Assistant and PCVs will review the audio record and confirm all notes. Below are described the recruitment and enrollment procedures for these data collection events.

Recruitment and Enrollment of Participants Followed within Households

We will utilize a random cluster sampling method to select ten (10) households in each of the three (3) sites per cluster. We will convenience sample one woman and one man in each of the households among those

who express a willingness to participate. We will ensure that the ten (10) chosen households fall within the households where the educational Care Group intervention takes place. Given that each Care Group will cover between 80 and 100 households, we are expecting to enroll participants from 10% of the households where the Care Group intervention occurs.

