
Recruitment and Enrollment of Participants Followed within Care Groups

We will utilize a random sampling method to select five (5) Care Group Volunteers in the Care Group of each the three (3) sites per cluster. We will seek to enroll, longitudinally follow, and collect data on three (3) younger woman (age 30 to 44) and two (2) older women (age 45 to 59) in each care group over the course of the study. Given that each Care Group has between 8 to 15 volunteers, we are expecting to enroll 1/3 to 1/2 of all Care Group Volunteers across all sites.

Detailed Care Group Volunteer sampling: While visiting a care group meeting, the RA will read the RESEARCH INFORMATION SHEET. The RA will then read the RECRUITMENT SCRIPT and ask the women if they are interested to participate. The RA will record the names of each younger woman (age 30 to 44) who is interested in participating on separate pieces of paper. The RA will fold each piece of paper separately and place into a container. The RA will blindly draw three names. The RA will then record the names of each older woman (age 45 to 59) who is interested in participating on separate pieces of paper. The RA will fold each piece of paper separately and place them into a container. The RA will blindly draw two names. The RA will

read the INFORMED CONSENT and SHORT FORM to each of the chosen participants separately and privately. The RA will obtain participant written consent with the SHORT FORM and will then enroll each participant by entering their contact information in the PARTICIPANT REGISTER. The RA will inform them separately of the data collection schedule.

Recruitment and Enrollment of Participants for Women's Focus Groups

We will conduct two focus groups every six (6) months. Five (5) care group members will be convenience selected from each care group AND two to three (2-3) household women participants will be convenience sampled to participate in a younger women's (age 30 to 49) and an older women's (age 45 to 59) focus group every six (6) months over the course of the study.

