Women. Criteria for inclusion include: 1) female Senegal citizen between the ages of 30 and 59, 2) Resident in Kedougou Region, 3) eligible to seek cervical cancer prevention services at a designated health structure in the Kedougou Region, Senegal, 4) willing to participate in survey or interview assessments; and 5) able to give informed consent.

Men. Criteria for inclusion include: 1) male Senegal citizen between the ages of 30 and 59, 2) Resident in Kedougou Region, 3) living in a household with at least one woman eligible to seek cervical cancer prevention services at a designated health structure in the Kedougou Region, Senegal, 4) willing to participate in survey or interview assessments; and 5) able to give informed consent.

Care Group Volunteer. Criteria for inclusion include: 1) Senegal citizen participating as a Care Group volunteer, 2) Resident in the Kedougou Region, Senegal, 3) willing to participate in survey or interview assessments, and 4) able to give informed consent.

Exclusion Criteria

Participants will be excluded if they are

- No additional exclusion criteria exist.

Excluded or Vulnerable Populations

Special considerations of the involvement of women and minorities and the justification of the exclusion of minors are detailed below.

The total planned enrollment / Inclusion of Women and Minorities

1. Planned distribution of participants by sex/gender, race, and ethnicity - The total planned enrollment is:
 - a. Aim 1: 15 women from Care Groups for each site (3) per cluster (3) = 135. Ten women from households for each site (3) per cluster (3) = 90. Ten men from households per site (3) per cluster (3) = 90. This equals a total of 315 individuals (225 women and 90 men). There are no new participants in the focus groups.
 - b. Aim 2: Individual interview (no new participants) + Focus Groups (no new participants) + Document Review (no human participants) = 0 new participants
 - c. Aim 3: Individual interview (no new participants) + Document Review (no human participants) = 0

Total participants = 315

Of these we estimate that there will be 225 women and 90 men. Based on general population numbers for the Kedougou Region in the country of Senegal, we anticipate that 100% of participants will be from African descent. All participants (women and men) will be African and have been included in the "Black" category.

2. Subject selection criteria and rationale for selection –

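### The protocol's only power statement does not reproduce: 15 women in each of 3 clusters gives at most about 53% power for a 10-point difference, and 15 per cluster is not the planned sample

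*Protocol*

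**What the plan says.** The power paragraph in section 6.0 names its method as "Using two independent proportion method of cluster randomization power analysis (PASS13") and concludes that "the 10% difference of the screening rate with assumed ICC 0.01 requires n=15 per each of 3 clusters", for 80% power at significance level 0.05. It gives no baseline screening rate and does not say whether the test is one- or two-sided.

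The design is described differently in section 2.0 (Overview of Study Data Collection): "we will conduct a cluster-randomized stepped wedge study across three representative clusters".

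The number of women per cluster appears in several places:

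- Section 3.0, Table 2, row a (baseline survey): "Women: 75 / cluster".
- Section 3.0, Table 2, row b (interval interview): "Women: 45 / cluster".
- Section 3.0, Aim 1 text on the interval interviews: "with the same women (up to 25) and the same 10 men in each site per cluster".
- Section 3.0, Care Group recruitment: "select five (5) Care Group Volunteers in the Care Group of each the three (3) sites per cluster".
- Section 4.0, total planned enrollment: "15 women from Care Groups for each site (3) per cluster (3) = 135".

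Ten household women per site are added to the volunteers in both section 3.0 and section 4.0.

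**The concern.** Three things are wrong with the sentence.

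1. **The sample size looks far too small for its own inputs.** A 10-point difference between two proportions normally needs many more than 45 people per group, even before clustering is allowed for.
2. **The method is for two parallel groups.** In this trial three clusters cross over in sequence, period effects must be estimated, and the same women are interviewed repeatedly.
3. **Fifteen per cluster is not what will be enrolled.** The documents point to 45 or 75.

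This is the only power statement in the protocol, so a reader cannot tell from it whether the trial can detect the difference it names. The conflict between 45 and 75 matters as well: at a 5% baseline with uncorrelated rounds, power for 10 points is below 80% with one figure and above it with the other.

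**Working it through.** **Inputs.** From section 6.0: power 80%, significance level 0.05, difference 10 points, ICC 0.01, m = 15 women in each of 3 clusters. The baseline is not given there, so these rates are assumptions taken from elsewhere in the protocol:

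- 0% and 1.9%: national rates in women over 50 and aged 40–49 (section 1.0).
- 5%: 2014 local campaign (section 1.0).
- 6.9%: all women aged 18–69 nationally (Background).

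**Attempt to reproduce the stated figure.** The generous reading counts all three clusters in each condition, although the trial has only three in total.

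- Design effect = 1 + (15 − 1) × 0.01 = 1.14.
- Effective n per condition = 3 × 15 / 1.14 = 39.5.
- Power = Φ[(0.10 − 1.96·s0) / s1], where s0 = √(2·p̄(1−p̄)/n), s1 = √((p1(1−p1) + p2(1−p2))/n), and p̄ is the mean of p1 and p2.
- 0% vs 10%: s0 = √(0.095/39.47) = 0.0491 and s1 = √(0.090/39.47) = 0.0478. Power = Φ(0.08) = 53%.
- 5% vs 15%: s0 = √(0.180/39.47) = 0.0675 and s1 = √(0.175/39.47) = 0.0666. Power = Φ(−0.49) = 31%.

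Two-sided pooled power at each cluster size:

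| Women per cluster | Effective n per condition | 0% | 1.9% | 5% | 6.9% |
|---|---|---|---|---|---|
| 15 (stated) | 39.5 | 53% | 42% | 31% | 28% |
| 45 | 93.75 | 89% | 78% | 63% | 56% |
| 75 | 129.3 | 96% | 89% | 77% | 70% |

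**Can the unstated inputs rescue it?** Over baselines from 0% to 90%, the maximum at 15 per cluster is 53% pooled and 55% unpooled (two-sided), or 66% and 67% (one-sided). All four maxima occur at 0%. An arcsine version gives 82% at exactly 0%, but 74% at 0.1%, 63% at 0.5% and 48% at 1.9%, so it succeeds only at the boundary.

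**Women per cluster needed on the named method.** With n the effective size required per condition, m = 0.99·n / (3 − 0.01·n).

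- 0%: n = 73.4, m = 32.1, so 33.
- 1.9%: n = 99.7, m = 49.2, so 50.
- 5%: n = 140.1, m = 86.7, so 87.

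Against the stated 15 this is 33/15 = 2.2-fold to 87/15 = 5.8-fold. One-sided, the figures are 24, 36 and 58.

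**What is planned.**

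- 5 volunteers + 10 household women = 15 per site; × 3 sites = 45 per cluster. This agrees with Table 2, row b.
- 15 volunteers + 10 household women = 25 per site; × 3 sites = 75 per cluster. This agrees with Table 2, row a, and with the ceiling of 25 per site in the Aim 1 text.

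**Illustration for the actual design.** This uses generalised least squares on cluster-period means with fixed period effects, crossovers before rounds 2, 3 and 4, ICC 0.01, total variance p̄(1−p̄), and a normal approximation. The comparison is 5% vs 15%. The number of rounds is varied from 4 to 7: section 3.0 says six, but baseline plus every six months for three years would count seven. The within-woman correlation r is an assumption.

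| Women per cluster-round | r = 0, 4 / 6 / 7 rounds | r = 0.5, 4–7 rounds |
|---|---|---|
| 45 | 62% / 65% / 66% | 85–91% |
| 75 | 81% / 85% / 86% | 97–99% |

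At 6 rounds and r = 0, the difference detectable with 80% power is 12.6 points with 45 women and 9.2 points with 75.

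**The case against.** The best defence is that the sentence contains a slip between site and cluster. Fifteen women per site is a planned number (ten household women plus five volunteers), and nine sites of 15 on the same formula give 95% power at 0%, 86% at 1.9% and 73% at 5%. This may well be where the 15 came from. But the sentence says clusters, the protocol defines these as three districts, and the reading still falls short of 80% at the local 5% figure.

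Some further points stand as qualifications:

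- **Table 2 can be read as consistent.** It lists 75 and 45 for two different instruments, and 25 per site is a ceiling. The harder conflict is five versus fifteen volunteers per site. It still leaves the interval-interview number unsettled.
- **The interviews are not the only Aim 3 source.** Aggregated health-service records also supply uptake and re-screening (Table 4), so a power statement based on interviews should say that it covers only those.
- **A two-group comparison is among the planned analyses** (section 6.0), so the named method is incomplete for this design rather than unrelated to it.
- **The stepped-wedge figures are illustrative.** A normal approximation with three clusters is optimistic: a t reference with 4 degrees of freedom lowers the two-proportion results from 53% and 31% to 36% and 21%. In the other direction, r = 0 is pessimistic for women interviewed repeatedly. A repeated-proportion model also does not represent first-time screening, which happens once per woman.
- **The Aim 3 target is much larger than 10 points.** For 5% versus 35%, the two-proportion formula gives 93% even at 15 per cluster, and both formulas give over 99% at 45 or 75.

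None of this makes the stated sample size correct.

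**Conclusion.** The concern holds. Read as written, 15 women in each of three clusters gives at most 53% two-sided pooled power for a 10-point difference, and 31% at a 5% baseline. It understates the women needed per cluster by about 2-fold (0% baseline) to 6-fold (5% baseline), two-sided. That rests on counting three clusters in each condition, ICC 0.01 and a z-test for two proportions. The failure does not depend on which baseline is assumed, apart from the arcsine exception at exactly 0%.

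This does not mean that the enrolled trial has 31% power. Whether it reaches 80% for 10 points at a 5% baseline depends on whether 45 or 75 women are interviewed per cluster-round and on the within-woman correlation. The power paragraph gives neither. The defect should be fixed, but it lies in the justification and in the conflicting enrolment numbers; the planned sample has not been shown to be too small for the trial's 35% target.

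**What to change.** First decide how many women per cluster take part in the interval interviews, and make Table 2, the Aim 1 text, the Care Group recruitment text and the section 4.0 enrolment count agree. Then replace the power sentence with one for the actual design, for example:

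> Power for the interview-based screening outcome was computed for a stepped wedge of three clusters with fixed period effects, [number] six-monthly rounds, [45 or 75] women interviewed per cluster-round, two-sided alpha 0.05, ICC 0.01, baseline screening rate [x]% and within-woman correlation [r]. The design has [y]% power for a 10-point difference and 80% power for a difference of [d] points.

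The statement should also say how the small number of clusters was allowed for. The stepped-wedge figures in the working are for orientation only and should not be pasted in.

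The cost is one recomputation, one reworded paragraph and the reconciliation of 45 and 75. No additional enrolment is proposed. The downside is that, with 45 women per cluster-round, uncorrelated rounds and a 5% baseline, the stated power for 10 points will fall below 80%.
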